- Vital signs at 1 hour and 1.5 hours post endotoxin injection
- Continuous IV infusion of 250 ml 0.9% saline over 1 hour
- 14 ml venous blood sample at 1 hour post endotoxin
- Urine sample at 1 hour post endotoxin
- 14 ml venous blood sample at 1½ hours post endotoxin

2 hours post-endotoxin injection

- Vital signs at 2 hours post endotoxin
- Continuous IV infusion of 250 ml 0.9% saline over 1 hour
- 23 ml venous blood sample at 2 hours post endotoxin
- Urine sample at 2 hours post endotoxin

3 hours post-endotoxin injection

- Vital signs at 3 hours post endotoxin
- 23 ml venous blood sample at 3 hours post endotoxin
- Bleeding time measurement at 3 hours post endotoxin

4 hours post-endotoxin injection

- Vital signs at 4 hours post endotoxin
- 14 ml venous blood sample at 4 hours post endotoxin
- Urine sample at 4 hours post endotoxin

6 hours post-endotoxin injection

- Vital signs at 6 hours post endotoxin
- 14 ml venous blood sample at 6 hours post endotoxin
- Urine sample at 6 hours post endotoxin
- Continuous cardiac monitoring ends

Visit 4 (Period 1, 1 day after visit 3)

- Telephone follow-up for adverse events
- Facility to convert to in-person visit if any concerns raised

There will then follow a washout period of at least 5 weeks, and not more than 18 weeks, between the first endotoxin challenge day and the beginning of the second medication period. This is to avoid reliably any tolerance of the response to endotoxin, a phenomenon absent by 5 weeks [39].

Visit 5 (10 to 14 days after visit 3)

- Telephone follow-up for adverse events

Visit 6 (Period 2, Day 0)

- Vital signs (BP, pulse, temperature)
- Physical examination
- Adverse event recording
- Concomitant medication recording
- Medically qualified investigator to confirm eligibility criteria again (see section 6) and that no withdrawal criteria (section 7.10) are met at this point prior to proceeding to medication period 2
- Laboratory safety blood tests: 12.5 ml venous blood for full blood count, urea & electrolytes (sodium, potassium, urea and creatinine), liver function tests, clotting screen
- Medication dispensed for period 2
- Dosing training for use of aspirin lysine if required

Participants will be advised to begin antiplatelet medication, allocated as follows, for period 2 from the morning after visit 6:

- If received no IMP in period 1, to receive no aspirin, but a loading dose of ticagrelor (180 mg) 1 hour before endotoxin injection in period 2.

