- Collect unused study medication and perform drug accountability check (sachet/pill count)
- Infusion of 250 ml 0.9% saline over 30 minutes
- 23 ml venous blood at 60 minutes after last dose of oral antiplatelet medication or equivalent time if not receiving IMP during period 1 (just before endotoxin administration)

0 hour (time of endotoxin injection)

- Continuous cardiac monitoring starts
- *E.coli* endotoxin 2 ng/kg intravenously administered over 1 minute
- Vital signs at 5, 15 and 30 minutes post-endotoxin
- Continuous IV infusion of 250 ml 0.9% saline over 1 hour
- 14 ml venous blood sample at 30 minutes post endotoxin

1 hour post-endotoxin injection

- Vital signs at 1 hour and 1.5 hours post endotoxin injection
- Continuous IV infusion of 250 ml 0.9% saline over 1 hour
- 14 ml venous blood sample at 1 hour post endotoxin
- Urine sample at 1 hour post endotoxin
- 14 ml venous blood sample at 1½ hours post endotoxin

2 hours post-endotoxin injection

- Vital signs at 2 hours post endotoxin

- Continuous IV infusion of 250 ml 0.9% saline over 1 hour
- 23 ml venous blood sample at 2 hours post endotoxin
- Urine sample at 2 hours post endotoxin

3 hours post-endotoxin injection

- Vital signs at 3 hours post endotoxin
- 23 ml venous blood sample at 3 hours post endotoxin
- Bleeding time measurement at 3 hours post endotoxin

4 hours post-endotoxin injection

- Vital signs at 4 hours post endotoxin
- 14 ml venous blood sample at 4 hours post endotoxin
- Urine sample at 4 hours post endotoxin

6 hours post-endotoxin injection

- Vital signs at 6 hours post endotoxin
- 14 ml venous blood sample at 6 hours post endotoxin
- Urine sample at 6 hours post endotoxin
- Continuous cardiac monitoring ends

Visit 8 (Period 2, 1 day after visit 6)

- Telephone follow-up for adverse events
- Facility to convert to in-person visit if any concerns raised

Visit 9 (Period 2, 10 to 14 days after visit 6)

- Telephone follow-up for adverse events

Study investigations will be performed at the following time points:*

*Baseline refers to visit 2, and the pre- and post-endotoxin samples are to be taken during both experimental periods.

- **Inflammatory markers and cytokines**
- TNF- α : Baseline, pre-last medication dose, pre-endotoxin and 0.5, 1, 1.5, 2, 3, 4 and 6 hours post-endotoxin
- IL-6: Baseline, pre-last medication dose, pre-endotoxin and 0.5, 1, 1.5, 2, 3, 4 and 6 hours post-endotoxin
- CRP: Baseline, pre-endotoxin and 6 hours post-endotoxin

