- **Prostanoids and Leukotrienes**
- Serum TXB₂: Baseline, pre-last medication dose, pre-endotoxin and 0.5, 1, 1.5, 2, 3, 4 and 6 hours post-endotoxin
- Urinary PGI-M: Baseline, pre-endotoxin and 1, 2, 4 and 6 hours post-endotoxin
- Urinary creatinine: Baseline, pre-endotoxin and 1, 2, 4 and 6 hours
- Serum PGE₂: Baseline, pre-endotoxin and 0.5, 1, 1.5, 2, 3, 4 and 6 hours post-endotoxin
- **Leucocyte phenotype and activation status**
- White blood cell count with differential leukocyte count: Baseline, pre-last medication dose, pre-endotoxin and 0.5, 1, 1.5, 2, 3, 4 and 6 hours post-endotoxin
- **Haemostasis**
- Bleeding time: Pre-endotoxin and 3 hours post-endotoxin
- **Platelet function tests**
- Light transmittance aggregometry (agonists: arachidonic acid 0.3 and 1 mmol/l, collagen 4 and 16 mg/ml, and ADP 20 μ mol/l): Baseline, pre-endotoxin and 3 hours post-endotoxin
- **Samples for storage**
- Plasma for storage: Baseline, pre-last medication dose, pre-endotoxin and 0.5, 1, 1.5, 2, 3, 4 and 6 hours post-endotoxin
- Serum for storage: Baseline, pre-last medication dose, pre-endotoxin and 0.5, 1, 1.5, 2, 3, 4 and 6 hours post-endotoxin
- DNA/RNA for storage: Baseline
- Urine for storage: Baseline, pre-endotoxin and 1, 2, 4 and 6 hours post-endotoxin

Details of fluid management

We anticipate that the total fluid load per volunteer will be 1000 ml over the 8 hours of the day at the NGH-CRF (250 ml preload and 750 ml infusion). The volunteers will also receive fluid boluses if required, which would be typically be in the range of 250-500 ml normal saline, given if mean arterial blood pressure is reduced by 20% or more or to maintain a systolic blood pressure over 100 mmHg and/or to relieve symptoms related to hypotension. Under normal circumstances, we would give a maximum of 1000 ml of

0.9% saline over 1 hour and a maximum of 2000 ml of 0.9% saline over the 8 hours of the day at the NGH-CRF.

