10.3.3 Secondary outcome analysis

Secondary analyses will be as follows:

Between aspirin dose regimens

1. Plasma TNF- α over time following endotoxin administration (measured at 0, 0.5, 1, 1.5, 2, 3, 4 and 6 hours post-endotoxin) assessed between aspirin groups (control vs. 20 mg BD vs. 75 mg OD vs. 300 mg OD, without ticagrelor) by two-way mixed ANOVA with treatment as a between-subjects factor and timepoint as a within-subjects factor.
2. Plasma IL-6 at 2 hours following endotoxin administration assessed between aspirin groups (control vs. 20 mg BD vs. 75 mg OD vs. 300 mg OD, without ticagrelor) by one-way ANOVA with treatment as a factor.
3. Plasma IL-6 over time following endotoxin administration (measured at 0, 0.5, 1, 1.5, 2, 3, 4 and 6 hours post-endotoxin) assessed between aspirin groups (control vs. 20 mg BD vs. 75 mg OD vs. 300 mg OD, without ticagrelor) by two-way mixed ANOVA with treatment as a between-subjects factor and timepoint as a within-subjects factor.
4. Change in serum CRP over time following endotoxin administration (measured at 0 and 6 hours post-endotoxin) assessed between aspirin groups (control vs. 20 mg BD vs. 75 mg OD vs. 300 mg OD, without ticagrelor) by one-way ANOVA.
5. Serum TXB₂ over time following endotoxin administration (measured at 0, 0.5, 1, 1.5, 2, 3, 4 and 6 hours post-endotoxin) assessed between aspirin groups (control vs. 20 mg BD vs. 75 mg OD vs. 300 mg OD, without ticagrelor) by two-way mixed ANOVA with treatment as a between-subjects factor and timepoint as a within-subjects factor.
6. Urinary PGI-M (measured at 0, 2, 4 and 6 hours, each adjusted for [divided by] urinary creatinine) over time following endotoxin administration assessed between aspirin groups (control vs. 20 mg BD vs. 75 mg OD vs. 300 mg OD, without ticagrelor) by two-way mixed ANOVA with treatment as a between-subjects factor and timepoint as a within-subjects factor.
7. Serum PGE₂ over time following endotoxin administration (measured at 0, 0.5, 1, 1.5, 2, 3, 4 and 6 hours post-endotoxin) assessed between aspirin groups (control vs. 20 mg BD vs. 75 mg OD vs. 300 mg OD, without ticagrelor) by two-way mixed ANOVA with treatment as a between-subjects factor and timepoint as a within-subjects factor.

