2. AUC of the graph of plasma TNF- α over time following endotoxin administration (measured at 0, 0.5, 1, 1.5, 2, 3, 4 and 6 hours post-endotoxin) compared between each aspirin regimen (control, 20 mg BD, 75 mg OD, 300 mg OD, each without ticagrelor) and each corresponding DAPT regimen (control, 20 mg BD, 75 mg OD, 300 mg OD, each with ticagrelor 90 mg BD) by paired t-tests.
3. Plasma IL-6 at 2 hours following endotoxin administration, compared between each aspirin regimen (control, 20 mg BD, 75 mg OD, 300 mg OD, each without ticagrelor) and each corresponding DAPT regimen (control, 20 mg BD, 75 mg OD, 300 mg OD, each with ticagrelor 90 mg BD) by paired t-tests.
4. AUC of the graph of plasma IL-6 over time following endotoxin administration (measured at 0, 0.5, 1, 1.5, 2, 3, 4 and 6 hours post-endotoxin) compared between each aspirin regimen (control, 20 mg BD, 75 mg OD, 300 mg OD, each without ticagrelor) and each corresponding DAPT regimen (control, 20 mg BD, 75 mg OD, 300 mg OD, each with ticagrelor 90 mg BD) by paired t-tests.
5. Change in serum CRP over time following endotoxin administration (measured at 0 and 6 hours post-endotoxin) compared between each aspirin regimen (control, 20 mg BD, 75 mg OD, 300 mg OD, each without ticagrelor) and each corresponding DAPT regimen (control, 20 mg BD, 75 mg OD, 300 mg OD, each with ticagrelor 90 mg BD) by paired t-tests.
6. AUC of the graph of serum TXB₂ over time following endotoxin administration (measured at 0, 0.5, 1, 1.5, 2, 3, 4 and 6 hours post-endotoxin) compared between each aspirin regimen (control, 20 mg BD, 75 mg OD, 300 mg OD, each without ticagrelor) and each corresponding DAPT regimen (control, 20 mg BD, 75 mg OD, 300 mg OD, each with ticagrelor 90 mg BD) by paired t-tests.
7. AUC of the graph of urinary PGI-M (measured at 0, 2, 4 and 6 hours, each adjusted for [divided by] urinary creatinine) over time following endotoxin administration compared between each aspirin regimen (control, 20 mg BD, 75 mg OD, 300 mg OD, each without ticagrelor) and each corresponding DAPT regimen (control, 20 mg BD, 75 mg OD, 300 mg OD, each with ticagrelor 90 mg BD) by paired t-tests.
8. AUC of the graph of serum PGE₂ over time following endotoxin administration (measured at 0, 0.5, 1, 1.5, 2, 3, 4 and 6 hours post-endotoxin) compared between each aspirin regimen (control, 20 mg

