#### 10.3.3 Secondary outcome analysis

Secondary analyses will be as follows:

Between aspirin dose regimens

1. Plasma TNF- $\alpha$  over time following endotoxin administration (measured at 0, 0.5, 1, 1.5, 2, 3, 4 and 6 hours post-endotoxin) assessed between aspirin groups (control vs. 20 mg BD vs. 75 mg OD vs. 300 mg OD, without ticagrelor) by two-way mixed ANOVA with treatment as a between-subjects factor and timepoint as a within-subjects factor.
2. Plasma IL-6 at 2 hours following endotoxin administration assessed between aspirin groups (control vs. 20 mg BD vs. 75 mg OD vs. 300 mg OD, without ticagrelor) by one-way ANOVA with treatment as a factor.
3. Plasma IL-6 over time following endotoxin administration (measured at 0, 0.5, 1, 1.5, 2, 3, 4 and 6 hours post-endotoxin) assessed between aspirin groups (control vs. 20 mg BD vs. 75 mg OD vs. 300 mg OD, without ticagrelor) by two-way mixed ANOVA with treatment as a between-subjects factor and timepoint as a within-subjects factor.

4. Change in serum CRP over time following endotoxin administration (measured at 0 and 6 hours post-endotoxin) assessed between aspirin groups (control vs. 20 mg BD vs. 75 mg OD vs. 300 mg OD, without ticagrelor) by one-way ANOVA.
5. Serum TXB2 over time following endotoxin administration (measured at 0, 0.5, 1, 1.5, 2, 3, 4 and 6 hours post-endotoxin) assessed between aspirin groups (control vs. 20 mg BD vs. 75 mg OD vs. 300 mg OD, without ticagrelor) by two-way mixed ANOVA with treatment as a between-subjects factor and timepoint as a within-subjects factor.
6. Urinary PGI-M (measured at 0, 2, 4 and 6 hours, each adjusted for [divided by] urinary creatinine) over time following endotoxin administration assessed between aspirin groups (control vs. 20 mg BD vs. 75 mg OD vs. 300 mg OD, without ticagrelor) by two-way mixed ANOVA with treatment as a between-subjects factor and timepoint as a within-subjects factor.
7. Serum PGE2 over time following endotoxin administration (measured at 0, 0.5, 1, 1.5, 2, 3, 4 and 6 hours post-endotoxin) assessed between aspirin groups (control vs. 20 mg BD vs. 75 mg OD vs. 300 mg OD, without ticagrelor) by two-way mixed ANOVA with treatment as a between-subjects factor and timepoint as a within-subjects factor.

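### Every planned urinary PGI-M analysis omits the 1-hour sample that is scheduled in both periods, and no reason is given

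*Protocol*

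**What the plan says.** **Collection.** The list of investigations in protocol section 7.7 reads "Urinary PGI-M: Baseline, pre-endotoxin and 1, 2, 4 and 6 hours post-endotoxin". The correction factor follows the same times: "Urinary creatinine: Baseline, pre-endotoxin and 1, 2, 4 and 6 hours". A note above that list says that "the pre- and post-endotoxin samples are to be taken during both experimental periods". The procedures for visit 3 and for visit 7 each include "Urine sample at 1 hour post endotoxin", and Appendix 1 marks a urine sample at 1 hour on both endotoxin days.

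**Analysis.** Item 6 of protocol section 10.3.3 (aspirin regimens) uses "Urinary PGI-M (measured at 0, 2, 4 and 6 hours, each adjusted for [divided by] urinary creatinine". Item 17 (regimens with ticagrelor) and item 16 of the later list (three-way mixed ANOVA) give the same times. So does item 5 of the premature-termination analyses in section 10.6 (mixed model). The paired comparison of aspirin alone with aspirin plus ticagrelor, item 7 of the later list, is "AUC of the graph of urinary PGI-M (measured at 0, 2, 4 and 6 hours". The SAP repeats all five, for example "Urinary PGI-M (measured at 0, 2, 4 and 6 hours" in its section 10.3.3.

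**Endpoint.** Protocol section 3.3 defines the PGI-M secondary endpoint as an AUC over 0 to 6 hours and lists no sampling times.

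**The concern.** A value that is scheduled, collected in both periods and correctable for creatinine has no place in any planned analysis, and neither document says why. PGI-M carries some weight in the rationale: protocol section 2 reads the pilot trend in prostacyclin metabolite as a sign of less COX2 inhibition with the 20 mg twice-daily regimen.

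The other markers sampled serially are treated differently. TNF-α, IL-6, TXB2, PGE2 and leukocyte count are analysed over time at every scheduled post-endotoxin time, including 1 hour. The same item list also has another timing mismatch: items 9 and 10 use 0 and 6 hours for bleeding time and aggregation, where section 7.7 gives 3 hours. This suggests that the list was not checked against the schedule, though it does not prove that the PGI-M omission was accidental.

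Three things are at stake:

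- some precision;
- how well the AUC follows the first two hours;
- an open choice between four and five times, in a trial where investigators know the allocation (section 7.4).

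**Working it through.** The plan states no figure on this point, so there is none to reproduce. The check sets collected times against analysed times and then works out what the gap does to an AUC. The 0-hour value is taken to be the pre-endotoxin urine.

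**1. Values unused**

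- Scheduled post-endotoxin times: 1, 2, 4, 6 h (four). Analysed: 2, 4, 6 h (three). Unused: 1/4 = 25% per challenge day, or 1/5 = 20% if the 0-hour sample is counted.
- Ceiling: 72 participants × 2 challenge days = 144 values.
- At the interim: section 10.6 expects 46 first and 37 second challenge days, 46 + 37 = 83 visits, so about 83 values.

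**2. Where an AUC is involved**

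Only the paired item 7 computes an AUC for PGI-M. The section 3.3 endpoint is also an AUC. Trapezoid weights, in hours:

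| Grid | 0 h | 1 h | 2 h | 4 h | 6 h |
|---|---|---|---|---|---|
| Planned | 1 | - | 2 | 2 | 1 |
| With 1 h | 0.5 | 1 | 1.5 | 2 | 1 |

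Five-point AUC minus planned AUC = 0.5·y0 + y1 + 1.5·y2 - y0 - 2·y2 = y1 - (y0 + y2)/2. This is zero if the course from 0 to 2 hours is a straight line.

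The documents give no PGI-M time course, so the following range rests on assumptions:

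- 2-hour level at 1.5 to 3 times baseline;
- 1-hour value at 0% to 125% of the 2-hour rise;
- response either sustained to 6 hours, or half remaining at 4 hours and none at 6.

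The planned AUC then lies between about 11% below and 9% above the five-point AUC. Both ends come from a 3-fold rise that has gone by 6 hours: 12 against 13.5 (-11.1%) and 12 against 11 (+9.1%). For AUC above baseline, the range is -20% to +20%.

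**3. Precision of the AUC**

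Assume equal variance σ² at each time and a common within-subject correlation ρ. Then Var(AUC)/σ² = (1 - ρ)·Σw² + ρ·(Σw)². Both grids have Σw = 6. Σw² is 1 + 4 + 4 + 1 = 10 as planned, and 0.25 + 1 + 2.25 + 4 + 1 = 8.5 with the 1-hour value.

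| ρ | Planned | With 1 h | SD ratio |
|---|---|---|---|
| 0 | 10.0 | 8.5 | 1.085 |
| 0.5 | 23.0 | 22.25 | 1.017 |
| 0.9 | 33.4 | 33.25 | 1.002 |

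**4. The other four analyses**

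Items 6, 17 and 16 and the section 10.6 model work on values over time, so they lose one time level and nothing more. In items 6 and 17, the treatment-by-time interaction has (4 - 1)(4 - 1) = 9 numerator degrees of freedom as planned, against (4 - 1)(5 - 1) = 12 with the 1-hour level. The variance of a participant's time-average, (1 + (k - 1)ρ)/k, at ρ = 0.5 is 0.625 for k = 4 and 0.600 for k = 5, a difference of about 4%.

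**The case against.** The strongest reply accepts the mismatch and disputes that it matters.

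- **A reader might infer that 15% of the information is thrown away**, since 8.5 is 15% below 10. That is a variance figure for fully independent errors. On the SD scale it is 8.5%, and it shrinks to almost nothing as correlation within a challenge day grows. The documents give neither variance nor correlation for PGI-M. Pairing removes stable differences between participants, but the same-day correlation stays unknown. Only the range can be claimed.
- **A reader might infer that the planned AUC misses the rise of the response.** The risk section (2.1) describes a general inflammatory response that peaks at 2 hours. Nothing says that urinary PGI-M follows that course, and a urine sample need not reflect a single moment. The AUC shift may be nil and may go either way.
- **A reader might infer that every PGI-M analysis suffers through the AUC.** Four of the five do not use one, and for those the gain is not assured: if the regimens do not differ at 1 hour, three more interaction degrees of freedom could dilute that test.
- **The omission may be deliberate**, since all ten statements of the times agree. That cannot be excluded, but consistency is not a reason, and none is stated. The 1-hour urine is also listed for storage, so unused in the planned analyses does not mean lost.

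These points limit the consequences. They leave the gap between schedule and analysis as it is.

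**Conclusion.** The point holds as a minor inconsistency in a secondary endpoint. The documents establish that the 1-hour PGI-M and creatinine values are scheduled in both periods, that no planned PGI-M analysis uses them, and that no reason is given. A quarter of the post-endotoxin values is left out.

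The effect on the AUC comparison cannot be fixed from the documents. The shift depends on an unknown time course. The precision loss lies between 0.2% and 8.5% of the error SD for correlations from 0.9 down to 0, under equal variances and a common correlation. The remaining PGI-M analyses lose one time level. The primary TNF-α analysis is not touched. The case for change is that the data are already scheduled and that naming the times in advance removes a free choice.

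**What to change.** Write 0, 1, 2, 4 and 6 hours in all five PGI-M analyses: items 6 and 17, paired item 7 and three-way item 16 of section 10.3.3, and item 5 of the premature-termination list in section 10.6. Do this in both the protocol and the SAP. Make it a dated change before the PGI-M data are examined, because the trial is open-label and has an interim analysis. If the 1-hour value was left out on purpose, keep the four times and state the reason.

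The cost is a wording change and its documentation. It needs no new visit, sample or assay, since PGI-M and creatinine are already scheduled at 1 hour.
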